This study has two primary objectives. First, to evaluate changes in respiratory drive and inspiratory effort—measured by Pocc, PMI, and P0.1—and corresponding Vt across varying levels of pressure support in surgical ICU patients after major abdominal surgery who require prolonged mechanical ventilation (>48 hours)⁽¹⁷⁾. Second, we aim to determine the incidence of inadequate assistance (active, quasipassive)⁽⁷⁾ in patients receiving PSV and explore its association with relevant clinical outcomes.

Study Design

This is a prospective, single-center, observational physiological study conducted in the surgical intensive care unit (ICU). A repeated-measures design is employed to systematically evaluate the effects of pressure support (PS) level adjustments on respiratory effort, drive, and diaphragmatic function in mechanically ventilated patients.

Study Population

Inclusion Criteria

- Adult patients (age ≥ 18 years) admitted to the surgical ICU.
- Recent major abdominal surgery requiring postoperative ICU care
- Receiving invasive mechanical ventilation for more than 48 hours
- Clinically stable, with no plan for extubation within 6 hours of study enrollment.

- Able to tolerate short-term adjustments in pressure support (PS) level as per protocol.

Exclusion Criteria

- Known neuromuscular diseases affecting respiratory muscle function.
- Hemodynamic instability requiring escalation of vasopressor support.
- Severe hypoxic respiratory failure requiring PEEP >10 cmH₂O or FiO₂ >60%.
- Deep sedation (Richmond Agitation-Sedation Scale [RASS] score < -3) or ongoing neuromuscular blockade.
- History of chronic obstructive pulmonary disease (COPD) or other obstructive lung diseases.

Intervention / Protocol

After confirming eligibility and obtaining informed consent (from patients or legally authorized representative), enrolled patients will undergo a standardized stepwise adjustment of pressure support (PS) levels while remaining in pressure support ventilation mode. During the protocol, Automatic Tube Compensation (ATC) will be turned off to avoid interference with respiratory measurements. This protocol was adapted from Doccia et al. ⁽⁷⁾. Measurements will be performed once daily for up to three consecutive days or until the patient is extubated—whichever occurs first.

Pressure Support Steps

Patients will be studied at six PS levels in the following sequence:

[figure not shown]
- Baseline PS (clinically set level)
- Baseline -6 cmH₂O
- Baseline -3 cmH₂O

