- Return to baseline PS
- Baseline +3 cmH₂O
- Baseline +6 cmH₂O

The order of the four non-baseline steps will be randomized for each patient using sealed envelopes, while the baseline PS step will be performed first and repeated last to assess measurement reproducibility.

At each pressure support (PS) level, a 2-minute stabilization period will be followed by three consecutive measurements of the following parameters: tidal volume (V_t), respiratory rate, P_{0.1}, P_{occ}, pressure muscle index (PMI), static compliance of the

respiratory system (Crs), and peripheral oxygen saturation (SpO_2). Vt , RR , P0.1 , Pocc , PMI , and Crs will be obtained from the ventilator, while SpO_2 will be recorded from the ICU monitor. PMI will be calculated as $\text{PMI} = \text{Pplat} - (\text{PEEP} + \text{PS})$, and Crs as $\text{Crs} = \text{Crs} = \text{Vt} / (\text{Pplat} - \text{PEEP})$. All values will be averaged across the three readings. **Figure 1. Study**

Protocol Flowchart

Measurements and Outcomes

Primary Outcome

- To evaluate changes in respiratory drive and inspiratory effort—quantified using P0.1, maximum negative occlusion pressure (Pocc), and pressure muscle index (PMI)—across varying levels of pressure support in adult surgical ICU patients after major abdominal surgery.

Secondary Outcomes

- To quantify the incidence of quasi-passive and active response patterns during pressure support ventilation, based on physiological criteria derived from patient responses.
- To assess the relationship between these ventilatory response patterns and clinical outcomes, including duration of mechanical ventilation, ICU length of stay, reintubation or non-invasive ventilation use, and ICU/hospital discharge disposition.

Definition of ventilatory response patterns:

- An active pattern is characterized by relatively stable V_t and plateau pressure despite reductions in pressure support, accompanied by a compensatory increase in PMI—indicating greater patient-driven effort. In contrast, a quasi-passive pattern is marked by a progressive decline in V_t and plateau pressure with little or no change in PMI, suggesting limited patient contribution to ventilation. ⁽⁷⁾
- As no standardized thresholds currently exist, these classifications will be determined post hoc based on individual response trends observed in the study dataset.

Data Collection

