All data will be prospectively collected during each predefined pressure support (PS) level (baseline, ± 3 cmH₂O, ± 6 cmH₂O), following a 2-minute stabilization period at each step. The following variables will be recorded:

1. Demographics and Baseline Clinical Data

- Age, sex, height, weight, BMI
- Primary diagnosis and operation
- APACHE II or SOFA score at ICU admission
- Time from intubation to enrollment (hours)
- Baseline ventilator settings (PEEP, FiO₂, baseline PS)
- Baseline arterial blood gas (ABG): pH, PaCO₂, PaO₂, HCO₃⁻, SaO₂

2. Ventilatory and Physiological Parameters (at each PS level)

- Tidal volume (Vt) – measured from ventilator display
- Respiratory rate – measured from ventilator
- Minute ventilation (MV) – calculated
- P_{0.1} – occlusion pressure at 0.1 seconds
- P_{occ} – airway pressure drop during inspiratory hold
- PMI – pressure muscle index calculated as P_{plat} – (PEEP + PS)
- P_{plat} – plateau pressure (via inspiratory hold)
- P_{peak} – peak inspiratory pressure
- Crs – static compliance: Vt / (P_{plat} – PEEP)
- SpO₂ – peripheral oxygen saturation (pulse oximetry)
- EtCO₂ – end-tidal CO₂ if available
- HR and MAP – heart rate and mean arterial pressure (non-invasive or arterial line)
- Use of accessory muscles – observational note
- Signs of distress or dyssynchrony – e.g., paradoxical breathing, anxiety, diaphoresis

4. Post-Protocol Clinical Follow-up

- Duration of mechanical ventilation after study (in hours)
- Need for reintubation or non-invasive ventilation within 48 h
- Total ICU length of stay (LOS)
- ICU and hospital discharge status
- Complications: VAP, barotrauma, unexpected weaning failure

Safety and Tolerability

The protocol allows immediate cessation of PS level changes and return to baseline settings if any of the following occur:

- Respiratory rate >35 breaths/min
- SpO₂ < 90%
- HR > 140 bpm or >30% change from baseline
- Signs of distress: diaphoresis, agitation, anxiety
- Hemodynamic instability

Sample Size

This is an exploratory physiological study using a repeated-measures design. Based on prior literature (Docci et al., 2023; Umbrello et al., 2015), a within-subject difference in

the pressure muscle index (PMI) of approximately 2.0 cmH₂O (standard deviation ~2.5) between pressure support (PS) levels is considered clinically meaningful.

Using a two-sided paired t-test with the following assumptions:

- Alpha (α) = 0.05
- Power (1 - β) = 0.90
- Effect size = 0.8

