The calculated minimum required sample size is 20 patients. To improve the precision of subgroup analyses, enhance generalizability, and account for possible dropouts or incomplete data, we plan to enroll a total of 40 patients.

Statistical Analysis

Descriptive statistics will be used to summarize baseline characteristics. Continuous variables will be presented as mean \pm standard deviation or median (IQR), depending on distribution. Categorical variables will be summarized as counts and percentages.

Primary analysis:

- Repeated-measures ANOVA or Friedman test (non-parametric) will be used to assess changes in PMI, Pocc, and P0.1 across PS levels.
- Post-hoc pairwise comparisons will be performed with Bonferroni correction.

Secondary analysis:

- Pearson or Spearman correlation will be used to evaluate relationships between effort indices (PMI, Pocc, P0.1).
- Linear mixed models will explore associations between PS levels and effort parameters, accounting for intra-patient variability.
- The incidence of under- and over-assistance will be described, and logistic regression may be used to assess their associations with clinical outcomes (e.g., prolonged ventilation).

A p-value <0.05 will be considered statistically significant. Statistical analyses will be performed using R.

Ethical Considerations

- Study protocol to be approved by institutional ethics board.
- Written informed consent obtained from patient or surrogate.
- Minimal risk as PS level adjustments are brief and within clinically accepted ranges.

References

1. van Oosten JP, Akoumianaki E, Jonkman AH. Monitoring respiratory muscles effort during mechanical ventilation. *Curr Opin Crit Care*. Feb 1 2025;31(1):12-20. doi:10.1097/mcc.0000000000001229

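### ICU stay is recorded as total stay, so part of the outcome has already elapsed when the response pattern related to it is first measured

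*Protocol*

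**What the plan says.** - **Use of the outcome.** Measurements and Outcomes, Secondary Outcomes: "To assess the relationship between these ventilatory response patterns and clinical outcomes, including duration of mechanical ventilation, ICU length of stay". The closing paragraph of the Background also places exploration of this association under the second of the study's two primary objectives.
- **What is recorded.** Data Collection, item 4 (Post-Protocol Clinical Follow-up): "Total ICU length of stay (LOS". The first item of that list is "Duration of mechanical ventilation after study (in hours".
- **When patients enter.** Inclusion Criteria: "Receiving invasive mechanical ventilation for more than 48 hours" and "Recent major abdominal surgery requiring postoperative ICU care". The first sets a floor and no ceiling. The second gives no number of days.
- **When the pattern is measured.** Intervention / Protocol, after enrolment: "Measurements will be performed once daily for up to three consecutive days or until the patient is extubated".
- **What is known about earlier time.** Data Collection, item 1, lists "Time from intubation to enrollment (hours". No section subtracts it from an outcome or names it as a covariate.
- **Analysis.** Statistical Analysis, secondary analysis: "logistic regression may be used to assess their associations with clinical outcomes (e.g., prolonged ventilation". No time origin is given.

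**The concern.** An outcome related to an exposure should start when the exposure is observed. Here the exposure is the response pattern, seen for the first time at the first study session. Total ICU stay starts earlier, by an amount that differs between patients and has no stated upper limit. The ventilation outcome in the same list does not have this problem, because it is counted after the study.

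Two things can follow. If patients with one pattern had on average been in the ICU longer before enrolment, total stay will differ by pattern even when the pattern predicts nothing afterwards. If prior time is unrelated to pattern, it only adds variance, which matters in a study of 40 patients. In either case a reported association between pattern and ICU stay would be hard to interpret as prognostic.

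**Working it through.** **The plan's own figure.** The Protocol computes nothing for ICU stay. Its one computed figure is the minimum of 20 patients for the paired PMI comparison, with effect size 2.0/2.5 = 0.8. By the noncentral t distribution, 19 patients give power 0.909 and 20 give 0.924, so that figure is sound. It does not bear on this point.

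**Structure.** Total stay = stay before the first session + stay after it. So the difference in mean total stay between patterns = (difference before) + (difference after). If the second term is zero, the first passes through unchanged.

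**Inputs.** From the Protocol: 40 patients, two-sided alpha 0.05, entry after more than 48 hours of ventilation. Everything else below is an assumption, because the Protocol gives no stay lengths, standard deviations or pattern frequencies.

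**Check 1: prior stay differs by pattern, no difference afterwards.** Assume 20 patients per pattern, SD after enrolment 5 d and SD before enrolment 3 d.
- SD of total stay = √(5² + 3²) = √34 = 5.83 d.
- SE of the difference = √(34 × 2/20) = √3.4 = 1.84 d.
- For a prior difference D, the approximate rejection rate is 1 − Φ(1.96 − D/1.84) + Φ(−1.96 − D/1.84). For D = 2, D/1.84 = 1.08 and the rate is about 19%.
- Simulation (mean stay after enrolment 7 d, two-sample t-test, 20,000 runs):

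| Prior difference (d) | Difference in total stay (d) | Rejected, total stay | Rejected, stay from enrolment |
|---|---|---|---|
| 0 | 0.0 | 4.7% | 4.9% |
| 1 | 1.0 | 8.4% | 4.7% |
| 2 | 2.0 | 19.6% | 5.0% |
| 3 | 3.0 | 36.8% | 4.8% |
| 4 | 4.0 | 57.4% | 4.9% |

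**Check 2: a different model and test.** The chance of a quasi-passive pattern rises with prior days on the logistic scale (slopes 0.2, 0.4, 0.6 per day). Prior time is 2 d plus an exponential, stay after enrolment has mean 8 d and SD 6.4 d, and the test is Mann-Whitney.
- Exponential mean 4 d: false positives for total stay about 18%, 37% and 54%. The average prior gaps between patterns are roughly 2.5, 3.8 and 4.7 d.
- Exponential mean 2 d: about 7%, 10% and 14%.
- Stay counted from enrolment: about 5% throughout.

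**Check 3: prior stay unrelated to pattern.** With the inputs of check 2 (exponential mean 4 d, so SD 4 d), the outcome variance rises from 6.4² = 41 to 41 + 4² = 57. The ratio is 57/41 = 1.39, and 40/1.39 = 28.8, so the cost is like losing about 11 of 40 patients. In terms of power, for an assumed true difference of 4 d after enrolment with SD 5 d, power is 70% with no prior variation and 68%, 63%, 50% and 37% at a prior SD of 1, 2, 4 and 6 d.

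**Check 4: does resetting the clock suffice?** The 5% in checks 1 and 2 follows from assuming that stay after enrolment is independent of time before it. If longer prior time also lengthens later stay, unadjusted stay from enrolment is confounded too. With the model of check 2 at exponential mean 4 d, its false-positive rate is about 7% to 12% under a modest assumed link, and up to about 29% under a stronger one.

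**The case against.** The item quoted is an entry in a data list. The outcome itself says only ICU length of stay, and a time origin or covariate for an exploratory association is often left to an analysis plan, which is not at hand. Recording total stay is not wrong in itself, and two list items with different origins do not contradict each other. The named analysis is an optional logistic regression whose example is prolonged ventilation, so the tests simulated above are not the Protocol's. The amount of confounding is assumed.

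Much of this stands, and it limits the point. It does not remove it: the Protocol does not leave the ICU variable open but specifies it as total, next to a neighbour that is counted after the study. A reader who follows the text will analyse total stay.

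Four stronger readings are tempting and are not supported:
- **That the Protocol's analysis has a false-positive rate of 19% or 57%.** Those rates belong to assumed inputs and to tests it does not name.
- **That long prior ventilation produces the quasi-passive pattern.** The Background says that over-assistance may promote diaphragm disuse. It does not link duration of ventilation to this pattern, and the direction of any bias is unknown.
- **That prior time is unlimited.** No ceiling is stated, but surgery must be recent, which is some limit even though it is undefined in days.
- **That everything needed for the fix is already listed.** No ICU admission, discharge or session dates appear in Data Collection, and time from intubation is not time from ICU admission.

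**Conclusion.** The point holds in a limited form. As written, the ICU-stay outcome includes time that elapsed before the response pattern was measured. The consequence is bias if prior stay differs by pattern and lost precision if it does not. That much follows from the definitions and needs no assumption.

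The size does need assumptions. With 40 patients and no true effect after enrolment, the Mann-Whitney false-positive rate runs from the nominal 5% with no link to about 55% with a strong one; the Protocol does not allow a choice within that range. The primary analysis and the sample size are unaffected. The association is listed as a secondary outcome in an exploratory study, patterns are classified post hoc, and the regression is optional. The change is worth making because it is cheap, not because a large error has been shown.

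**What to change.** For the association with response pattern:
1. Define ICU stay as days from the first study session to ICU discharge.
2. Report total ICU stay descriptively only.
3. Adjust the association for the intubation-to-enrolment time already collected. It is only a proxy for ICU time before enrolment, but without it the new clock can still be confounded (check 4).

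The cost is one or two sentences in the outcome and analysis sections. The first session date and the ICU discharge date must be kept on the case report form; total stay already requires the latter, and daily sessions are dated in any case. One covariate is spent in a model of 40 patients, which is a real but acceptable loss. No procedure and no sample size changes.

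### Is the minimum of 20 patients too small because it ignores the Bonferroni correction in the primary analysis?

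*Protocol*

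**What the plan says.** The Sample Size section of the protocol starts from PMI. A within-patient difference in "the pressure muscle index (PMI) of approximately 2.0 cmH₂O (standard deviation ~2.5) between pressure support (PS) levels is considered clinically meaningful". The calculation is introduced with "Using a two-sided paired t-test with the following assumptions", which are "Alpha (α) = 0.05", power 0.90 and an effect size of 0.8. It ends with "The calculated minimum required sample size is 20 patients". Enrolment is then set at twice that number. The reasons given are subgroup precision, wider applicability and the need to "account for possible dropouts or incomplete data, we plan to enroll a total of 40 patients". No loss rate is stated.

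Under Primary analysis, the Statistical Analysis section lists first an omnibus test (repeated-measures ANOVA or Friedman) for PMI, Pocc and P0.1 across support levels, and then: "Post-hoc pairwise comparisons will be performed with Bonferroni correction". The number of pairs and the pairwise test are not given.

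Data Collection refers to "each predefined pressure support (PS) level (baseline, ± 3 cmH₂O, ± 6 cmH₂O", which is five distinct levels. The protocol section on the steps counts six because "the baseline PS step will be performed first and repeated last to assess measurement reproducibility".

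**The concern.** The quantity used for sizing is a difference between two support levels. The only level-to-level tests listed under the primary analysis are Bonferroni-corrected, so each is run at an alpha below 0.05. A minimum computed at the full 0.05 therefore does not match the tests it appears to support.

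Five levels give four comparisons with baseline (alpha 0.05/4 = 0.0125) or ten pairs in all (alpha 0.05/10 = 0.005). If 20 were the working sample size, the study would fall short of its own 90% target for its own 2.0 cmH₂O difference. The doubling to 40 is also justified on other grounds than multiplicity, so the spare 20 patients look like a free reserve when the correction has already used part of it.

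**Working it through.** **Inputs.** From Sample Size: difference 2.0, SD 2.5, two-sided alpha 0.05, power 0.90, effect size d = 0.8, minimum 20, enrolment 40. Since 2.0/2.5 = 0.8, the SD is read as that of the paired difference; the protocol does not say so in words. From Data Collection: five distinct levels. Assumed, because the protocol does not fix it: a family of m = 4 or m = 10 pairs within PMI.

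**Formula.** Power = P(|T| > t(1 − α/2m; n − 1)), where T is noncentral t with n − 1 degrees of freedom and noncentrality d√n.

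**1. The plan's own figure (m = 1).** The normal approximation gives ((1.960 + 1.282)/0.8)² = 16.4, so 17. The exact test gives 89.2% at n = 18, 90.9% at n = 19 and 92.4% at n = 20. The exact minimum is 19, so 20 is sound for the test named.

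**2. With Bonferroni, separate paired t-tests.** Noncentrality is 0.8√20 = 3.58 at n = 20 and 0.8√40 = 5.06 at n = 40.

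| Pairs | Alpha per pair | Power, n = 20 | n for 90% | Power, n = 40 | Patients that can be lost from 40 |
|---|---|---|---|---|---|
| 1 | 0.05 | 92.4% | 19 | 99.9% | 21 |
| 4 | 0.0125 | 78.3% | 26 | 99.1% | 14 (35%) |
| 10 | 0.005 | 65.5% | 31 | 97.7% | 9 (22.5%) |

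One patient fewer misses the target in each corrected row: n = 25 gives 89.2% for four pairs, and n = 30 gives 89.8% for ten.

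**3. Wider families.** Counting the repeated baseline as a sixth level gives 15 pairs: 33 patients needed, 96.7% power at 40. Correcting ten pairs across all three indices gives 30 tests: 36 needed, 94.4% at 40. Forty is enough in both.

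**4. Pooled ANOVA error instead of separate SDs.** With 4(n − 1) degrees of freedom and sphericity assumed, the requirement is 24 (four pairs) or 28 (ten pairs), and n = 20 gives 84.3% or 75.1%. So 26 and 31 are not unique answers; they depend on a pairwise test that the protocol does not name. Rank-based pairs after a Friedman test would give other figures again.

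**5. The omnibus test, which is listed first.** Assume compound symmetry, so the error variance is 2.5²/2 = 3.125 and the noncentrality is n·Σ(μ − mean)²/3.125, with 4 and 4(n − 1) degrees of freedom. At n = 20:

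- Two levels 2.0 apart and the other three midway: Σ = 2.0, noncentrality 12.8, power about 80%.
- Linear trend of 2.0 from lowest to highest level: Σ = 2.5, noncentrality 16, power about 89%.
- Linear trend with the +6 and −6 levels each 2.0 from baseline: Σ = 10, noncentrality 64, power above 99%.

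At n = 40 the first and least favourable of these patterns has noncentrality 25.6 and power of about 99%.

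**The case for a change.** The best case for a change is that this is not a detail left to an analysis plan. The calculation and the correction rule both stand in the protocol, and they disagree. A reader told that 20 is the minimum could suppose that half the enrolment may be lost with 90% power intact for the corrected pairs, when 78.3% or 65.5% would remain. Incomplete sequences are foreseeable, since the safety rules allow the steps to be stopped and the protocol itself expects some incomplete data. A sentence or two would put it right at no cost in patients.

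The disagreement stands, and so does its direction: every correction tried needs more than 20. The consequence does not stand. The protocol never says that 20 covers the corrected pairs, states no loss rate that could prove wrong, and plans nothing at 20. Sizing an exploratory physiological study on one representative contrast and then protecting the follow-up pairs is ordinary practice. Putting 26 or 31 in the text would also present as fixed a number that depends on a family and a test the protocol leaves open.

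Two limits remain. If 2.5 were the SD at a single level, the answer would turn on the within-patient correlation: at 0.5 nothing changes; at 0.3, 40 patients give 94.6% (four pairs) or 89.4% (ten); at 0, 82.5% or 72.2%. The stated effect size of 0.8 argues against that reading. And differences below 2.0 have less power at 40 (for 1.5 cmH₂O, 87.4% or 78.7%), but the protocol does not set them as targets.

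**Conclusion.** The observation is correct but calls for no change. Twenty is a valid minimum for the single uncorrected comparison that the Sample Size section describes; it is not a minimum for the Bonferroni-corrected pairs, which would need about 24 to 26 patients for four comparisons with baseline or 28 to 31 for all ten pairs. The planned 40 covers both, with at least 97.7% power for a 2.0 cmH₂O pair and room to lose 9 to 14 patients on the separate paired t-tests before power drops below 90%. Correcting over 15 pairs or 30 tests still leaves more than 94% at 40.

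This rests on 2.5 being the SD of the paired difference and on PMI pairs that truly differ by 2.0 cmH₂O. It says nothing about power for Pocc, P0.1, subgroups or the outcome regressions. Within those bounds, rewording the minimum would leave enrolment, analysis and conclusions as they are.

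### Holm would be a cheap improvement on Bonferroni for the pairwise pressure support comparisons; the power gained is uncertain, and Bonferroni is not an error

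*Protocol*

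**What the plan says.** The primary analysis (Protocol, Statistical Analysis) is a repeated-measures ANOVA or Friedman test of PMI, Pocc and P0.1 across pressure support (PS) levels. It is followed by: "Post-hoc pairwise comparisons will be performed with Bonferroni correction". The number of comparisons in the family is not given.

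Under Data Collection, "All data will be prospectively collected during each predefined pressure support (PS) level", and the levels listed are baseline, ±3 and ±6 cmH2O, which makes five distinct settings. Baseline is performed twice, so there are six steps.

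The Sample Size section takes a within-patient PMI difference of about 2.0 cmH2O, with "standard deviation ~2.5) between pressure support (PS) levels is considered clinically meaningful". It does not say which two levels are meant. The calculation is introduced by "Using a two-sided paired t-test with the following assumptions", with "Alpha (α) = 0.05", "Power (1 - β) = 0.90" and "Effect size = 0.8". The result is that "The calculated minimum required sample size is 20 patients"; 40 are to be enrolled. The section calls the study exploratory.

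**The concern.** The PS settings are ordered. If effort falls steadily as support rises, the widest gaps give the largest differences and are rejected easily. Bonferroni still charges the smallest gaps for all 10 tests. Holm charges each test only for the hypotheses not yet rejected, so easy rejections at wide gaps relax the threshold for narrow ones.

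The 3 cmH2O steps carry the finest information on where effort changes with support, and they are the pairs most likely to be missed. Holm uses the same p-values and needs no extra data, so for hypothesis testing Bonferroni gives up power for nothing. What has to be established is how much.

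**Working it through.** **The plan's own figure.** Effect size = 2.0/2.5 = 0.8. Exact power of a two-sided paired t-test at alpha 0.05 (noncentral t, n − 1 degrees of freedom, noncentrality 0.8√n) is 0.909 at n = 19 and 0.924 at n = 20. The stated minimum of 20 is reproduced to within one patient.

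**The family.** Five levels give 5 × 4/2 = 10 pairs: four gaps of 3 cmH2O, three of 6, two of 9 and one of 12. Bonferroni tests each at 0.05/10 = 0.005. If the repeated baseline counted as its own step there would be 6 × 5/2 = 15 pairs, each at 0.0033.

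**The two rules.** Bonferroni rejects pair i if p ≤ 0.05/10. Holm orders the p-values and compares the k-th smallest with 0.05/(11 − k), stopping at the first failure. Its first threshold is 0.005 and later ones are larger, so it cannot lose a Bonferroni rejection. If all six wider pairs have been rejected, the next pair is tested at 0.05/4 = 0.0125. Familywise error is held at 5% under any dependence. In simulation with no PS effect and 10 pairs, both methods erred in 4.2% of trials.

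**Power for neighbouring 3 cmH2O steps.** All 10 paired t-tests were simulated; only the steps that truly change are averaged. The documents supply the 2.0, the 2.5 and the 40. The shape of the trend and the split of the spread are assumptions:

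- Spread A: patient slope SD 0.3 per cmH2O, residual SD 1.22. The SD of a 6 cmH2O difference is √[(6 × 0.3)² + 2 × 1.22²] ≈ 2.5.
- Spread B: slope SD 0.2, residual SD 1.55. √[(6 × 0.2)² + 2 × 1.55²] ≈ 2.5.
- Spread C: SD 2.5 for every pair, with no slope variation.

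| Assumed mean PMI change, n = 40 | Spread | Bonferroni | Holm | Gain (points) |
|---|---|---|---|---|
| Linear, 2.0 per 3 cmH2O step | C | 97.7% | 99.9% | 2 |
| Linear, 1.5 per step | C | 79.1% | 95.6% | 16 |
| Linear, 1.0 per step | C | 34.2% | 56.4% | 22 |
| Linear, 0.5 per step | C | 5.5% | 8.2% | 3 |
| Linear, 1.0 per step (2.0 per 6 cmH2O) | A | 61% | 84% | 23 |
| Linear, 1.0 per step | B | 44% | 69% | 25 |
| Linear, 0.75 per step (1.5 per 6 cmH2O) | A | 31% | 51% | 20 |
| 1.0 per step, below baseline only | A | 60% | 67% | 7 |
| 1.0 per step, below baseline only | B | 43% | 51% | 8 |
| 1.0 at the lowest step only | A | 61% | 62% | 1 |
| 1.0 at the lowest step only | B | 44% | 45% | 1 |

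The 0.75 row rests on spread A; a wider spread lowers both powers and the gain there.

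**Fewer evaluable patients.** At n = 20 with 2.0 per step (spread C), power is 65.6% with Bonferroni and 90.4% with Holm. At n = 30 with 1.0 per step, it is 43% against 68% (spread A) and 29% against 48% (spread B).

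**Does 40 absorb Bonferroni?** For a true difference of 2.0 (SD 2.5), 90% power at alpha 0.005 needs 31 patients, and 33 with 15 pairs. Both are below 40.

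**The case against.** The strongest case for leaving the text alone has four parts.

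- Bonferroni is a valid, prespecified correction in a study that calls itself exploratory, and it gives matching simultaneous intervals directly. This stands: nothing in the inference is wrong.
- No document makes the neighbouring steps the key contrasts. The omnibus test comes first, the pairwise tests are post hoc, and linear mixed models across PS levels are planned as a secondary analysis. This also stands and limits what is at stake, though the pairwise tests remain part of the primary analysis.
- The large gains need a linear trend over the whole range, the shape most favourable to Holm. If the interest is where effort starts to change, part of the range is flat and the gain falls to about 0 to 8 points. The protocol gives no reason to assume linearity: its Background describes a window within which patients modulate effort, and its quasi-passive pattern has PMI nearly constant.
- The planning difference is not tied to any pair of levels. Placed on each neighbouring step, it leaves Bonferroni at 97.7%.

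On the other side, placing 2.0 on every neighbouring step is equally an assumption; it implies a mean change of 4 × 2.0 = 8 cmH2O from −6 to +6. Since PMI = Pplat − (PEEP + PS), a patient with fully stable Pplat shifts PMI by about 3 cmH2O per step and a quasi-passive patient by about 0. An even mix would average about 1.5 and one third active about 1.0, where the gains are 16 and 22 points. Those mixes are illustrative, as the protocol gives no proportions. The protocol also allows for incomplete data, and its safety rules permit stopping the PS changes, so fewer than 40 complete sets is possible.

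A reader might infer that Bonferroni loses much of the power for the 3 cmH2O steps outright. The documents do not support that unconditionally: on one permissible reading of the protocol's own difference, SD and sample size, the loss is about 2 points. A reader might also infer that 40 patients are too few because the minimum of 20 was calculated at an unadjusted 0.05. For a difference of 2.0 that does not follow, since 31 to 33 patients suffice after correction.

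**Conclusion.** A cheap improvement, not an error. For testing, Holm is never worse than Bonferroni at the same familywise error. At 40 patients the gain for neighbouring steps is about 2 points, about 0 to 8 points, or about 20 to 25 points under, respectively, the full planning difference on each step, change over part of the range, or a linear change of about 0.75 to 1.0 cmH2O per step. The protocol does not say which applies, so no single figure should be quoted. Linear steps as small as 0.5 cmH2O gain little, because both methods then have almost no power.

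These results cover PMI only, with a family of 10 pairs per index, roughly normal data, paired t-tests, complete cases and one measurement day per patient. Pocc, P0.1 and the Friedman route were not quantified. That Holm rejects whatever Bonferroni rejects holds for them too; the size of the gain does not carry over.

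**What to change.** In Statistical Analysis, Primary analysis, replace *Bonferroni correction* with *Holm correction* for the pairwise PS comparisons within each index. Where simultaneous confidence intervals are reported, keep Bonferroni intervals and say so.

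The cost is one word plus that sentence, with no extra data or patients. The one real downside is that Holm gives no simple matching intervals, so a pair can be significant under Holm while its Bonferroni interval still includes zero; a short note in the results would cover this.
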